11.2.1 Primary Analysis of Secondary Endpoints

The primary analysis for the secondary endpoints will be based on the PPS for the non-inferiority tests and FAS for the superiority tests for Ex-U.S. and FAS for U.S.

11.2.1.1 Hb

The first secondary efficacy endpoint for the US submission and the Ex-US submission will be the primary efficacy endpoint for the Ex-US submission and the US submission, respectively. The Ex-US secondary efficacy endpoint will use MMRM model described in 11.1.3.1. The US first secondary efficacy endpoints will use the same statistical analysis methodology for the primary efficacy endpoint for Ex-US.

11.2.1.2 Mean change from baseline in LDL cholesterol averaged over Weeks 12-24

The mean change from baseline in LDL cholesterol averaged over Weeks 12-24 will be compared between the 2 treatment groups using the MMRM model with baseline LDL cholesterol as a covariate, treatment group, visit, interaction of visit and treatment group, and the above-mentioned 4 stratification factors as fixed effects. The same strategy as that used in MMRM for Hb will be used to choose variance covariance structure. Data up to visit of Week 52 will be included in the model. The estimates for difference of LDL Cholesterol averaged over Weeks 12 to 24 between the two treatment groups will be generated from an estimate statement from Visit Week 12 to 24. Superiority will be declared if the upper bound of the 2-sided 95% confidence interval of the difference between roxadustat and Epoetin alfa (roxadustat - epoetin alfa) is less than 0.

11.2.1.3 Mean change from baseline in Hb levels between Weeks 18 to 24 in patients whose baseline CRP> ULN

Change from baseline in Hemoglobin from baseline to the average level during the Week 18 to 24 will be analyzed using the ANCOVA MI as the primary endpoints. Both Non-inferiority of roxadustat vs. Epoetin and superiority will be tested. The non-inferiority margin is fixed as a difference of -0.75.

11.2.1.4 Average monthly IV iron use during 28 to 52 Weeks

The average monthly IV iron use during the treatment period will be calculated for monthly intervals. The treatment period will be divided in periods of 28 days and for each of these periods the monthly mean of IV iron will be used using the following formula:

Monthly iron use for each subject = Total IV iron in mg / [(last visit date – first drug date +1)/ 28]

The average monthly iron use will be compared between the 2 treatment groups using an ANCOVA model adjust for baseline iron replete, treatment group and above-mentioned stratification factors as fixed effects. Superiority will be declared if the lower bound of the 2-

sided 95% confidence interval of the difference between Epoetin alfa and roxadustat exceeds 0.

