### 7.2 Secondary Endpoints

- **US (FDA) submission:** The proportion of subjects who achieve a Hb response at two consecutive visits during the first 24 weeks of treatment, without rescue therapy within 6 weeks prior to the Hb response.

A Hb response is defined, using central laboratory values, as

- Hb  $\geq 11.0$  g/dL and a Hb increase from baseline by  $\geq 1.0$  g/dL in subjects whose baseline Hb  $> 8.0$  g/dL, or
- Increase in Hb  $\geq 2.0$  g/dL in subjects whose baseline Hb  $\leq 8.0$  g/dL

- **Ex-US submission:** Mean Hb change from baseline to the average level during the Evaluation Period, defined as Week 28 until Week 36 without rescue therapy within 6 weeks prior to and during the evaluation period. This analysis will be based on the PPS population.

Both, US and ex-US Submissions:

- Average monthly IV iron use per subject during the Treatment Period. Mean change in low-density lipoprotein (LDL) cholesterol averaged over Weeks 12 to 24.

- Blood pressure effects:
  - Proportion of subjects with exacerbation of hypertension, meeting at least one of the following criteria:
    - Increase in BP: An increase from baseline of  $\geq 20$  mm Hg systolic BP and sBP  $>170$  mmHg, or an increase from baseline of  $\geq 15$  mm Hg diastolic BP and dBP $>100$  mmHg. Increases from baseline in blood pressure must be confirmed by repeat measurement.
  - Time to an increase in BP as defined above.
  - Mean change in mean arterial pressure (MAP) averaged over Weeks 8 to 12.
- Time to achieve first Hb response as defined by the primary endpoint (ex-US) (which is the secondary endpoint for the US [FDA]).

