1 INTRODUCTION

This statistical analysis plan (SAP) provides a more technical and detailed elaboration of the statistical analyses of efficacy and safety as outlined and/or specified in the final study protocol. Specifications of tables, figures, and data listings are contained in a separate document (Table shells).

A separate pooled-analysis SAP for pre-specified analysis based on adjudicated composite safety data will complement this study specific SAP. This SAP is based on the Amendment 4 of the protocol dated September 20, 2017.

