4.3 SECONDARY EFFICACY ENDPOINTS

The secondary efficacy endpoints are for both US and Ex-US submissions unless specified otherwise:

US (FDA submission): The proportion of subjects who achieve a Hb response at two consecutive visits with at least 5 days apart during the first 24 weeks of treatment, without rescue therapy within 6 weeks prior to the Hb response. This analysis will be based on the ITT Population.

A Hb response is defined, using central laboratory values, as

- Hb ≥ 11.0 g/dL and a Hb increase from baseline by ≥ 1.0 g/dL in subjects whose baseline Hb > 8.0 g/dL, or
- Increase in Hb ≥ 2.0 g/dL in subjects whose baseline Hb ≤ 8.0 g/dL

Ex-US submission: Mean Hb change from baseline to the average level during the Evaluation Period, defined as Week 28 until Week 36 without rescue therapy within 6 weeks prior to and during the evaluation period. This analysis will be based on the PPS population.

- The time to achieve the first hemoglobin (Hb) response defined by the primary endpoint for Ex-US or the first secondary efficacy endpoint for the US submission.
- Proportion of patient exposure time (months) with Hb ≥ 10 g/dL during Weeks 28-52, similarly analysis for the period between Weeks 28 - 36
- Mean change from baseline in Low-density lipoprotein (LDL) cholesterol averaged over Weeks 12-24
- Mean change from baseline in Hb levels between Weeks 18 to 24 in patients whose baseline hs-CRP $>$ ULN
- Average monthly IV iron use per subject during weeks 28-52
- Time to first RBC transfusion during the treatment
- Mean change in mean arterial pressure (MAP) averaged over Weeks 8-12

- Time to first exacerbation of hypertension (defined as [systolic BP ≥ 170 mmHg AND systolic BP increase from BL ≥ 20 mmHg] or [diastolic BP ≥ 110 mmHg AND diastolic BP increase from BL ≥ 15 mmHg]) during weeks 28 to 52

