11.2 ANALYSIS OF SECONDARY ENDPOINTS

The secondary endpoints are for both U.S. and Ex-U.S. submission unless otherwise specified. Once the primary hypothesis has been rejected for the primary endpoint, the secondary endpoints in the order that was specified in section 4.3 will be tested using a fixed sequence testing procedure, in order to maintain the overall two-sided type I error of 0.05. If p-value from a test is < 0.05, the claim of superiority or non-inferiority will be considered successful and the test will progress to the next comparison in sequence as follows.

Table 5 Key Secondary Endpoints Fixed Sequence Testing Procedure

Test	Variable	Comparison
1	Proportion of subjects who achieve an Hb response at two consecutive visits during the first 24 weeks of treatment, (U.S.) or the mean Hb change from baseline to the average level during the Evaluation Period, defined as Week 28 until Week 52 for Ex-U.S..	Non-inferiority of roxadustat versus EPO. The non-inferiority margin for the difference of responder analysis between groups is 0.15 The non-inferiority margin for the difference of average of Change in Hb values between groups is - 0.75 g/dL.
2	LDL cholesterol change from BL to the average of weeks 12 to 24.	Superiority of roxadustat versus EPO
3	Mean change from baseline in Hb levels between Weeks 18 to 24 in patients whose baseline CRP > ULN:	The non-inferiority with margin of - 0.75 of roxadustat versus EPO
4	Monthly IV iron (mg) use per subject during weeks 28 to 52.	Superiority of roxadustat versus EPO
45	Time to first RBC transfusion during the treatment.	Non-inferiority of roxadustat versus EPO with Non-inferiority margin of 1.8
5	Change from BL to the average MAP of weeks 8 to 12	Superiority of roxadustat versus EPO
6	Time to first exacerbation of hypertension (defined as [systolic BP \geq 170 mmHg AND systolic BP increase from BL \geq 20 mmHg] or [diastolic BP \geq 110 mmHg AND diastolic BP increase from BL \geq 15 mmHg]) during weeks 28 to 52	Superiority of roxadustat versus EPO & Non-inferiority with margin of 1.8

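### SAP 11.2.1.4 does not restrict the IV iron calculation to Weeks 28–52, the window its endpoint names, and leaves the end date of the averaging time undefined

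*SAP*

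**What the plan says.** The protocol (Synopsis and 7.2) defines the endpoint as "Average monthly IV iron use per subject during the Treatment Period".

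The SAP narrows the window. Section 4.3 lists "Average monthly IV iron use per subject during weeks 28-52", Table 5 Test 4 reads "Monthly IV iron (mg) use per subject during weeks 28 to 52", and the heading of 11.2.1.4 repeats those weeks. The SAP also states: "This SAP is based on the Amendment 4 of the protocol dated September 20, 2017". The narrower window is therefore not left over from another protocol version.

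The body of 11.2.1.4 reads differently. It opens with "The average monthly IV iron use during the treatment period will be calculated for monthly intervals". It continues with "The treatment period will be divided in periods of 28 days and for each of these periods the monthly mean of IV iron", and then gives one formula per subject: "Monthly iron use for each subject = Total IV iron in mg / [(last visit date – first drug date +1)/ 28" (closing bracket omitted here). The comparison is an ANCOVA, with superiority declared if the lower 95% limit for epoetin alfa minus roxadustat exceeds zero. Under SAP 11.2.1 a superiority test uses the FAS.

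SAP 11.3.4.3 applies the same analysis to the second and third years of treatment and adds no window.

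**The concern.** The only derivation given for the endpoint does not calculate the endpoint. It takes all IV iron and divides by all time from the first drug date. Neighbouring sections do select their window: for LDL (SAP 11.2.1.2) the estimate "will be generated from an estimate statement from Visit Week 12 to 24", and the MAP section (11.2.1.5) names its visit weeks in the same way.

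The end of the averaging time is also open. The last visit could be the end-of-treatment visit, the end-of-study visit 4 weeks later (protocol 6.1.3.1), or one of the contacts every 3 to 6 months after early termination (protocol 6.1.2.6). SAP 16.2.7 uses the same term, also without a definition.

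IV iron use is a stated secondary objective. Three further tests follow Test 4 in the fixed sequence (RBC transfusion, MAP, hypertension) and are reached only if it succeeds. The trial is open-label. Protocol 8.4.5 wants the SAP final before much data accumulate, with significant changes highlighted. The visible SAP text does not flag this change of window.

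**Working it through.** The documents give no iron-use rate, SD or power for this endpoint, so there is no planned figure to reproduce. All mg rates below are assumptions for illustration.

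**1. Which window does each place give?**

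| Place | Window |
|---|---|
| Protocol Synopsis, 7.2 | Treatment Period |
| SAP 4.3; Table 5 Test 4; heading of 11.2.1.4 | Weeks 28–52 |
| SAP 11.2.1.4, opening sentence | treatment period |
| SAP 11.2.1.4, formula | first drug date to an undefined last visit |
| SAP 11.3.4.3 (years 2 and 3) | same formula, no window |

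Taken literally, one formula returns the same number for Weeks 28–52, year 2 and year 3.

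**2. Share of the averaging time inside the window.** With a last visit at Week T (T at least 52), the share is 24/T.
- T = 52: 24/52 = 46%
- T = 104: 24/104 = 23%
- T = 156: 24/156 = 15%
- Leaving before Week 28: 0%. Such a subject still gets a score. At 200 mg per 28 days, stopping at Week 20 gives 5 × 200 × 28/141 = 198.6, although no Weeks 28–52 value exists.

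**3. When the arm comparison is not affected.** Suppose both arms use iron at twice their later rate before Week 28, and the last visit is Week 52 for everyone. Later rates are 100 (epoetin alfa) and 50 (roxadustat).
- Epoetin alfa: (7 × 200 + 6 × 100) × 28/365 = 153.4
- Roxadustat: (7 × 100 + 6 × 50) × 28/365 = 76.7

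Every score is multiplied by the same constant, 1.534. Difference and standard error scale together, so a test against zero is essentially unchanged. A time pattern that adds the same amount in both arms cancels from the difference.

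**4. When it is affected: time pattern differs by arm.** Epoetin alfa is constant at 100, so its total to Week 52 is 1300. The last visit is Week 52.

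| Roxadustat rate before / after Week 28 | True window difference | Formula difference |
|---|---|---|
| 100 / 50 | 50 | (1300 − 1000) × 28/365 = 23.0 |
| 150 / 50 | 50 | (1300 − 1350) × 28/365 = −3.8 |
| 50 / 100 | 0 | (1300 − 950) × 28/365 = 26.8 |

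**5. When it is affected: follow-up differs by arm.** Both arms use 200 before and 100 after Week 28, so the window difference is 0. If one arm's last visit is Week 52 and the other's Week 104:
- Week 52: 2000 × 28/365 = 153.4
- Week 104: (7 × 200 + 19 × 100) × 28/729 = 126.7
- Difference: 26.7

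**6. Undefined last visit.** If the visit 4 weeks after treatment ends the count and no iron from those weeks is included, the score falls to 20/24 = 83% of its value after 20 weeks of treatment, and to 52/56 = 93% after 52 weeks. These figures are conditional. The numerator has no cut-off either, and SAP 10 counts concomitant medication to 28 days after the last dose.

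**The case against.** The strongest reply is that the intended window is plain. Three places name Weeks 28–52, and the sentence on 28-day periods could be a step towards averaging periods 8 to 13, which would give the stated endpoint. That stands as a reading of intent. It does not repair the derivation, because nothing selects those periods and the formula runs from first dose.

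A reader might go further than the documents allow in four ways.

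- **The two averages support the same test only if iron use is constant over time.** Step 3 shows otherwise. Large ratios between individual scores are not evidence of a changed test.
- **The formula is the protocol endpoint carried over.** It is close, but if the last visit falls after treatment the denominator runs past the Treatment Period.
- **The SAP has one convention, ending at the last dose, that only needs restoring.** SAP 5.4 and 11.3.4.1 do end there. The Efficacy Emergent Period (SAP 11) and hospitalisations (SAP 11.3.2) can run to 7 days after it.
- **The sponsor concealed the change, or it favours roxadustat.** Some front pages of the SAP were removed before review, so only the visible text can be said not to flag the change. Nothing in the documents shows a direction.

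**Conclusion.** The defect is confirmed and should be fixed. As written, SAP 11.2.1.4 computes a different quantity from the endpoint named in SAP 4.3, Table 5 and its own heading, and it matches the protocol's window only approximately.

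On nominal weeks, the stated window is between 46% and 15% of the averaging time for last visits from Week 52 to Week 156. Test 4, and access to the three tests after it, can change under any of three conditions: the time pattern of use differs by arm, the length of follow-up differs by arm, or varying follow-up reweights subjects. Treatment length varies by design, from possibly under 52 weeks to about 3 years after the last randomisation. Even so, whether any of these conditions holds to an important degree cannot be judged from the documents. The size and direction of the effect on Test 4 are unknown, and the mg examples show only what is possible.

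**What to change.** 1. Replace the formula with IV iron (mg) given on treatment in Weeks 28–52, divided by (on-treatment days in Weeks 28–52 / 28). Both parts must cover the same stated days. One choice is 28-day periods 8 to 13: Day 7 × 28 + 1 = 197 to Day 13 × 28 = 364, which is 168 days. This leaves out Day 365, the scheduled Week 52 day. The Table 9 visit windows would instead span Days 183 to 378 (196 days). The choice has to be written down.
2. Replace the last visit date with one defined on-treatment cut-off, used in numerator and denominator alike.
3. State before database lock how FAS subjects with no on-treatment time in the window are handled. Do not code them as 0, which would count them as using no iron.
4. Record the change of window from the protocol.
5. Give SAP 11.3.4.3 its own windows, for example Days 365–728 and Days 729–1092 (13 periods of 28 days each).

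Reporting the protocol's whole-treatment rate as a sensitivity analysis is optional.

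The cost is one changed derivation, one rule and one line of record. It assumes that IV iron records hold the amount by administration date, which the documents do not state, so records that straddle a window boundary need a rule. The downside is that subjects who leave before Week 28 have no observed value in the window.

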## 1.2 Treatment of Anemia

Today, therapy with erythropoiesis-stimulating agents (ESAs) is a major alternative to transfusion in managing anemia associated with CKD. For those not resistant to ESAs, parenteral administration of exogenous recombinant human EPO (epoetin alfa or beta) or pegylated analogues has been a widely accepted approach for treatment of anemia in patients with CKD (Winearls, 1986; Eschbach, 1989; Eschbach, 1987), despite the documented safety risks. These safety risks include hypertension, thrombosis and cerebrovascular events and may be associated with the supraphysiologic plasma EPO levels frequently observed with ESA therapy. Anemic patients with CKD or ESRD will require life-long treatment with these agents.

Although the treatment of anemia in CKD and ESRD is thought to contribute positively to a patient's quality of life, several studies in ESRD and CKD nondialysis patients have shown higher mortality or trends in that direction in the higher-dosed ESA-treated cohorts when the protocol objective was to treat to high target Hb levels (Besarab, 1998, Drueke, 2006; Singh, 2006). An ESA dose relationship to mortality has been reported in a review of the USRDS database (Zhang, 2004) of ESRD patients who received higher ESA doses. Additionally, ESA therapy for anemia in ESRD patients on HD usually requires concomitant intravenous (IV) iron supplementation. IV iron is associated with its own set of risks, including anaphylaxis.

There is currently an unmet medical need for an oral treatment that can correct anemia in CKD nondialysis and dialysis patients while avoiding supraphysiologic levels of circulating plasma EPO levels, and also minimizes the use of IV iron.

[figure not shown]
Roxadustat is an oral medication that could potentially deliver effective treatment for CKD-related anemia with less need for IV iron supplementation and without producing supraphysiologic levels of circulating EPO, which may translate into an improved safety profile.

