#### 1.4.2.2 Studies in Subjects with DD-CKD

Data from a 12-week study in incident-dialysis (48 HD and 12 PD) subjects (Study FGCL-4592-053), using similarly tiered, weight-based doses as Study FGCL-4592-041 demonstrated increases in mean Hb of approximately 2 g/dL after 6 weeks of treatment. Subjects were randomized to receive either no iron, oral iron or IV iron. The Hb responses were indistinguishable between the oral and IV iron arms; subjects in the no iron arm had a similar Hb response during the first 8 weeks of treatment, with plateauing during the last 4 weeks of treatment, suggesting that with long-term roxadustat treatment, iron supplementation may be necessary, however, oral iron appears to be as effective as IV iron, and is recommended as the first-line treatment in Phase 3. Starting roxadustat doses between 1.0 and 1.6 mg/kg appeared adequate to correct Hb in these subjects. In addition to Hb response, in this study, statistically significant ( $p < 0.001$ ) improvements of 5 to 10% overall average in the 36-Item Short Form Health Survey (SF-36) Physical Functioning, Role physical, and Vitality scores, as well as in the Functional Assessment of Cancer Therapy-Anemia (FACT-An) anemia and total scores were noted in the roxadustat-treated subjects. Significantly, these improvements were more pronounced (33% on average and up to 100%) in subjects with low BL scores ( $< 35$ ), and improvement was time-dependent. Also, in this study, roxadustat transiently lowered total cholesterol by about 20 mg/dL on average. Importantly, highly significant low-density lipoprotein (LDL) cholesterol reduction was also observed.

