#### 3.6.2.2 Intravenous Iron Supplementation

Intravenous iron supplementation is permitted if in the opinion of the Investigator the subject's Hb has not responded adequately and the subject is considered iron deficient.

Treatment with study medication will continue during IV iron administration. Discontinuation of IV iron is recommended once the subject is no longer deemed iron deficient (eg, ferritin  $\geq 100$  ng/ml [ $\geq 220$  pmol/L], TSAT  $\geq 20\%$ ) and has evidence of a hematopoietic response.

Note: IV iron administration in study subjects during hospitalization is not considered a protocol deviation.

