This efficacy endpoint will be analyzed using a mixed model of repeated measures (MMRM) with Hb baseline value as covariate and treatment group and randomization stratification factors as fixed effects and MI ANCOVA as sensitivity analysis for Ex-US submission.

This null hypothesis will be rejected if the two-sided 95% CI for the difference of least square means from the mixed model is above -0.75 g/dL.

Hb values under the influence of a rescue therapy within 6 weeks prior to and during this 8-week evaluation period will be censored in the analysis.

- The average monthly iron use will be compared between the 2 treatment groups using an ANCOVA model with baseline iron replete as a covariate, and treatment group and randomization stratification factors as fixed effects. Superiority will be declared if the lower bound of the two-sided 95% CI of the difference between epoetin alfa and roxadustat exceeds zero.
- Mean change from baseline in LDL cholesterol averaged over Weeks 12 to 24 will be analyzed using an MMRM model with baseline LDL cholesterol as a covariate and treatment group, visit, visits by treatment arm, and randomization stratification factors as fixed effects. Superiority will be declared if the lower bound of the two-sided 95% CI of the difference between epoetin alfa and roxadustat exceeds zero.

- Proportion of subjects with exacerbation of hypertension, meeting at least 1 of the following criteria will be analyzed using CMH model adjusting for treatment group and stratification factors
  - Increase in blood pressure: An increase from baseline in systolic blood pressure (sBP) of  $\geq 20$  mm Hg and sBP  $> 170$  mmHg or an increase from baseline in diastolic blood pressure (dBP) of  $\geq 15$  mm Hg and dBP  $> 100$  mmHg. Increases from baseline in blood pressure must be confirmed by repeat measurement.

Noninferiority of roxadustat vs. epoetin alfa will be tested. Non-inferiority will be declared if the upper bound of the two-sided 95% CI of the hazard ratio is less than 1.3.

- Time to an increase in blood pressure (defined as an increase from baseline of  $\geq 20$  mm Hg systolic BP and sBP  $> 170$  mmHg or an increase from baseline of  $\geq 15$  mm Hg diastolic BP and dBP  $> 100$  mmHg). Time to an increase in blood pressure will be analyzed using the Cox Proportional Hazards model adjusting for treatment group and randomization stratification factors. Superiority of roxadustat vs. epoetin alfa will be tested.

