5.4 ADDITIONAL DATA HANDLING RULES AND PRESENTATION SPECIFICATIONS

The following general guidelines will apply to all statistical analyses and data presentations:

- Baseline is defined as the last available value obtained prior to the first dose of study drug, unless otherwise specified in this SAP.
- Hb baseline is defined as the mean of the at least last three available values obtained prior to the first dose.
- Baselines for reticulocyte count, reticulocyte hemoglobin content (CHr), hepcidin, serum iron parameters (transferring, TIBC, TSAT, Ferritin, sTfR, and iron), lipids, blood pressures and heart rate are defined as the mean of values obtained within 6 weeks prior to the first dose.
- Randomization stratification factors and enrollment protocol version derived from actual data (not the ones from the randomization system) will be used in all applicable analysis models.

The stratification factors to be used in efficacy analyses are:

1. Us vs Ex-US Screening Hb values (≤ 8 g/dL vs. > 8 g/dL) (other than Hb related endpoints)
2. Cardiovascular/cerebrovascular/thromboembolic medical history (Yes vs. No)
3. Geographic Region
4. The original protocol and amended protocols

- Unscheduled visits within an allowable window will be grouped into the closest scheduled visits based on the visit window specified in Appendix 1. For subjects who have more than one measurement at a certain scheduled visit, the last measurements

will be used, with the exception of CPK, WBC, liver function tests (i.e., ALT, AST, GGT, ALP, and total bilirubin), in which the maximum measurement will be used.

- By default, US conventional units will be used for laboratory value presentations. A set of lab summary tables in SI units will also be provided based on TLF index.
- Age is calculated as of date that the informed consent form was signed.
 - age = INTCK('YEAR', Birth date, date of Informed Consent, 'C') where INTCK is a SAS function.
- Duration of treatment or days in treatment is calculated as: last dose date – first dose date +1
- Body weight, height and temperatures will be converted using the following formula:
 - kg = lb/2.2
 - cm = 2.54 x in
 - C° = (5/9) x (F° – 32)
- The mean, standard deviation and median will be presented with adding one more decimal to raw data with rounding off. The minimum and maximum will be presented with the same number of decimals as in the raw data.

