7 DEMOGRAPHICS AND OTHER BASELINE CHARACTERISTICS

Demographic parameters and important baseline and disease characteristics will be summarized by treatment group for the ITT, Safety, FAS and PPS populations. These include but may not be limited to age, age group (18 to 64, 65 to 74, ≥ 75), sex, ethnicity, race, region, weight, body-mass index (BMI), Hemoglobin, baseline Hb categories, iron repletion status at baseline, Ferritin, Ferritin group (<100 vs. ≥ 100 ng/mL), TSAT and TSAT group ($<20\%$ vs. $\geq 20\%$), iron deplete (ferritin ≥ 100 and TSAT $\geq 20\%$) vs. not, cHepcidin $<$ eligibility threshold or not, baseline C-reactive protein (CRP) group (CRP \leq ULN vs. CRP $>$ ULN), cardiovascular or cerebrovascular or thromboembolic medical history (yes vs. no), primary reason for CKD/ESRD as one of the baseline characteristics (DM and HPT vs. all others).

In addition, 25%-75% values of Hb and platelets will be presented. Frequency distributions (number and percentage of subjects) will be presented for categorical variables.

The baseline characteristics, iron indices, and iron IV given between ESA naïve and those treated with ESA then washed out will be summarized and presented in a table.

Descriptive statistics of baseline values for other parameters will be presented in their change from baseline tables.

A summary table for the patient population for enrolled patients before and after the protocol amendments will be presented.

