11.3.3 Missed Dialysis Sessions

Missed dialysis sessions are collected in the Dialysis Modality Form of the eCRF. For each subject, an entry will be recorded for missing dialysis. The number of missing dialysis will be summarized by treatment group.

The following missing dialysis-related data will be analyzed and compared between the 2 treatment groups:

- Occurrence (number) of missed dialysis sessions. The number of missed dialysis sessions for each subject will be collected. The mean number of missed dialysis sessions will be analyzed and compared between the 2 treatment groups using Mantel-Haenszel mean score test adjusting for stratification factors.
- Proportion of subjects with missed dialysis sessions. The proportion of subjects missed dialysis sessions will be compared between the 2 treatment groups using CMH model and stratified by the baseline stratification factors.
- Number of days of missed dialysis sessions per patient-exposure year (PEY). The number of days of missed dialysis sessions for each subject will be calculated (# of missed dialysis/weekly prescribed dialysis frequency* 7), where weekly prescribed dialysis is TIW in this study. The mean number of days of missed dialysis sessions will be analyzed and compared between the 2 treatment groups using the Mantel-Haenszel mean score test adjusting for stratification factors.

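### The IV iron superiority test is valid but leaves precision unused: it adjusts for iron status through a two-class repletion term only and omits dialysis modality.

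*SAP*

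**What the plan says.** The two documents agree on the model. SAP 11.2.1.4 specifies an "ANCOVA model adjust for baseline iron replete, treatment group and above-mentioned stratification factors as fixed effects", and protocol 8.4.3.2 an "ANCOVA model with baseline iron replete as a covariate, and treatment group and randomization stratification factors as fixed effects". SAP 11.3.4.3 reuses the analysis for the second and third years of treatment.

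Neither sentence says how repletion is coded. SAP 7 and SAP 13 treat it as a two-class status: ferritin and TSAT both at or above threshold, or not. SAP 7 labels the class that meets both thresholds as depleted: "iron deplete (ferritin ≥ 100 and TSAT".

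The factors listed in SAP 5.4 are region, screening Hb, cardiovascular history and protocol version ("The original protocol and amended protocols"). Dialysis modality is not among them, and no analysis model in either document includes it.

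The trial holds more baseline information than this. SAP 5.4 defines a continuous baseline for ferritin and TSAT. Inclusion criterion 3 admits both HD and PD subjects. SAP 11.3.3 refers to a modality form: "Missed dialysis sessions are collected in the Dialysis Modality Form of the eCRF".

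**The concern.** Protocol 3.6.2.2 permits IV iron when the investigator judges that Hb has not responded adequately and that the subject is iron deficient. It then says "Discontinuation of IV iron is recommended once the subject is no longer deemed iron deficient", with ferritin and TSAT as the example criteria. Protocol 1.2 adds that "ESA therapy for anemia in ESRD patients on HD usually requires concomitant intravenous (IV) iron supplementation". Iron stores and modality are therefore plausible predictors of the outcome. The model reduces the first to one split and ignores the second.

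The plan handles its other endpoints differently. The US primary ANCOVA (SAP 11.1.2) drops the two-class screening Hb factor and uses continuous baseline Hb. The LDL and MAP tests (SAP 11.2.1.2 and 11.2.1.5) adjust for continuous baselines.

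What is at stake is power. In SAP Table 5 the transfusion, MAP and hypertension tests come after IV iron, so a failure here ends formal testing of those three.

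**Working it through.** **Stated power.** With 300 per arm and a two-sided 5% level:
- US primary (SAP 5.1: difference -0.30, margin -0.75, SD 1.25). The distance to the margin is 0.75 - 0.30 = 0.45, and the standard error is 1.25 × √(2/300) = 0.102. Power = Φ(0.45/0.102 - 1.96) = 99.3%.
- Ex-US primary (80% in both arms, margin 15 points). The standard error is √(2 × 0.16/300) = 0.0327. Power = Φ(0.15/0.0327 - 1.96) = 99.6%.

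Both agree with the stated figure of at least 99%. Neither covers IV iron, for which no effect, SD or power is given. In general, 300 per arm gives 80% power for a difference of (1.96 + 0.84) × √(2/300) = 0.23 SD, and 500 per arm for 0.18 SD.

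**What a two-class term keeps.** If a normally distributed iron index is split so that a share q is replete, the split keeps φ(c)²/[q(1 - q)] of the variance the index explains, where c is the cut-point.

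| Share replete | R² kept |
|---|---|
| 50% | 64% |
| 70% | 58% |
| 80% | 49% |
| 90% | 34% |

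**What modality adds.** With PD share p and an HD-PD difference of d within-group SDs, modality R² = p(1 - p)d²/[1 + p(1 - p)d²]. For p = 0.2 and d = 0.5 this is 0.04/1.04 = 0.038.

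**Combined effect.** Variance ratio = (1 - iron R² - modality R²)/(1 - iron R² × share kept). This treats iron and modality as uncorrelated with each other and with the factors already in the model. For the second row below: (1 - 0.05 - 0.038)/(1 - 0.05 × 0.576) = 0.912/0.971 = 0.939. Power from an 80% start is Φ(2.80/√ratio - 1.96).

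Every input is assumed. The only guide to the PD share is a Phase 2 study (protocol 1.4.2.2): "Data from a 12-week study in incident-dialysis (48 HD and 12 PD) subjects", or 12/60 = 20%.

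| Replete | Iron R² | PD | d | Modality R² | Variance ratio | CI width ratio | N matching 600 | Power from 80% |
|---|---|---|---|---|---|---|---|---|
| 70% | 0.02 | 10% | 0.2 | 0.004 | 0.988 | 0.994 | 593 | 80.5% |
| 70% | 0.05 | 20% | 0.5 | 0.038 | 0.939 | 0.969 | 563 | 82.4% |
| 70% | 0.10 | 20% | 0.5 | 0.038 | 0.914 | 0.956 | 548 | 83.4% |
| 80% | 0.10 | 20% | 0.8 | 0.093 | 0.849 | 0.921 | 509 | 86.0% |
| 90% | 0.15 | 20% | 0.8 | 0.093 | 0.798 | 0.893 | 479 | 88.0% |

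**Check on a realistic outcome.** Monthly IV iron is likely to be skewed with many zeros. A simulation of such an outcome (600 subjects, 3,000 runs, 75% replete, 20% PD) compared a model with the two-class term alone against one that added the continuous index and modality. The variance ratio was 0.94 and power rose from 66% to 68%. One-sided type I error was about 2% under both models.

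**The case against.** The strongest reply is that nothing is broken. The ANCOVA is pre-specified, the trial is randomized, and chance imbalance in iron stores or modality is ordinary random error that the confidence interval already covers. This stands. A reader might infer that the estimate is biased or the test invalid, but the documents do not support that.

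The size is also open, and several stronger inferences fail:
- **The split is lopsided.** Inclusion criteria 6 and 7 suggest most subjects are replete. But they also admit subjects below threshold after supplementation without retest, and repletion needs both thresholds. The split is unknown.
- **Ferritin and TSAT alone trigger IV iron.** Protocol 3.6.2.2 also requires an inadequate Hb response and relies on the investigator's opinion.
- **Baseline iron predicts use well.** The endpoint is headed Weeks 28 to 52, months later. The baseline averages six weeks that may span supplementation.
- **Modality matters by a known amount.** Protocol 1.2 offers one qualitative sentence about ESA-treated HD patients and no comparison with PD. The 20% share comes from 60 Phase 2 subjects. Gains also shrink if region or another planned factor carries the same information.
- **Home HD belongs with PD.** The sentence cited concerns HD, so it does not support that grouping.

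Two further points stand. SAP 5.1 mentions approximately 1000 subjects, which lowers the practical stakes. And the formula in SAP 11.2.1.4 divides by the span from first drug to last visit, although its heading says Weeks 28 to 52; that needs settling separately.

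The objection that extra covariates are mere preference does not stand, because the plan already uses continuous baselines for Hb, LDL and MAP.

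**Conclusion.** The point holds as a loss of precision in a valid test. The planned model uses one two-class iron term and no modality term, while the trial has fuller baseline data that plausibly bear on the outcome.

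Under the assumed ranges, the fuller model would reduce the variance of the comparison by about 1% to 20%. That equals 7 to 121 of 600 subjects, a confidence interval about 0.6% to 11% narrower, or 0.5 to 8 power points from an 80% start. The upper end needs strong predictors and a 90/10 split. If baseline iron only weakly predicts later use, the gain is near zero. Whether the IV iron test has power to spare cannot be judged from the documents. The case for acting rests on the low cost and the place in the fixed sequence, not on a demonstrated large loss.

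**What to change.** Amend SAP 11.2.1.4, and with it 11.3.4.3, before data are reviewed by arm. The study is open-label, so covariates chosen later would not be credible.

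- Add baseline ferritin (log scale) and TSAT as continuous covariates, using the baseline in SAP 5.4, in place of or beside the repletion term.
- Add baseline dialysis modality, HD versus PD, as a fixed effect. State which eCRF field supplies it and how home HD is classed, since the schedule of assessments lists no separate modality item.
- Keep the planned stratification factors.
- If the repletion term stays, correct the reversed label in SAP 7 before it is coded.

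The cost is a short SAP edit and a few extra model terms. Ferritin and TSAT are already measured before dosing, and modality has to be known for eligibility.
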